4.4.1 Primary Efficacy Endpoint

The primary efficacy objective for this study is to evaluate the efficacy of MTAU9937A compared with placebo on the basis of CDR-SB change from baseline at Week 73 (with baseline defined as the average of available measurements before first dose which is expected to include both screening and baseline values).

The estimand of interest (the mITT estimand) is the mean absolute difference in CDR-SB change from baseline at Week 73 between active drug and placebo. It will be estimated using all randomized patients who received at least one dose of study drug, regardless of adherence to the assigned study treatment or to the protocol.

The MMRM approach described in Section 4.4 should provide a reasonable estimate of the mITT estimand. Mean change from baseline will be estimated at each post-baseline timepoint for each study arm (placebo and each treatment arm) using least squares means and 95% confidence intervals. The absolute difference in mean change from baseline will be estimated for each treatment arm compared with placebo using least-squares mean estimates from the MMRM model along with 95% confidence intervals.

4.4.2 Secondary Efficacy Endpoints

Secondary endpoints listed below will similarly be analyzed and reported using the methods described in Section 4.4.1 using the MMRM model described in Section 4.4. The secondary endpoints for this study are listed below:

- Change in ADAS-Cog13 score from baseline to Week 73
- Change in ADCS-ADL score from baseline to Week 73
- Change in RBANS total score from baseline to Week 73
- Change in Amsterdam iADL score from baseline to Week 73

4.4.3 Sensitivity Analyses

Mixed-models for repeated measures (MMRM) methods have been selected for the primary and secondary analyses due to their ability to accommodate the potential effects of missing data. An advantage of such models is that they rely on the assumption that the missing data mechanism is missing-at-random (MAR), rather than the more restrictive assumption that it is missing-completely-at-random (MCAR).

To evaluate the robustness of MMRM analyses to potential effects of missing data and validity of the MAR assumption, sensitivity analyses will be performed in the mITT population for the co-primary and secondary endpoints. At each time point (Week 25, Week 49, and Week 73), an ordinary least squares model for the change scores at that timepoint will be fit to estimate the treatment effect. These models will have terms for the baseline value of the endpoint, APOE4 strata, dementia status strata, the interaction between APOE4 strata and dementia status strata, baseline age, and treatment effect. These models will be fit using the following imputations for missing data:

- No imputation (a completer analysis)
- Using linear extrapolation imputation based on the values at baseline and the last week with a non-missing value
- Using last-observation-carried-forward
- Tipping point analysis

Intercurrent events may also influence the primary endpoint even if they do not directly result in missing data. Additional sensitivity analyses will be conducted using the above methods, but treating data collected after a given intercurrent event as missing. Proposed intercurrent events include missed study drug administration and initiation or modification of AD symptomatic concomitant medications. A separate section detailing intercurrent events and protocol deviations due to COVID-19 is included below. We propose to apply the same set of sensitivity analyses listed above when considering this additional set of intercurrent events.

Additional analyses looking at treatment effect estimates in subpopulations of patients receiving at least a minimum number of doses will also be conducted to assess if any observed treatment effect could have been potentially diluted by patients who did not fully adhere to the study drug administration schedule.

COVID-19 Sensitivity Analyses

Trial conduct in the double-blind period of most TAURIEL subjects up until their respective Week 49 visits was unimpacted by COVID-19, with roughly 1/3 of subjects completing the entire double-blind period with zero impact. For subjects that were still active in the double-blind period during the COVID pandemic, the following additional measures were taken to mitigate the effect of COVID-19 on drug exposure and data collection:

- Some subjects received blinded study drug administration remotely at their homes. Adverse events were also collected at these visits.
- A subset of COAs, including CDR-SB and ADCS-ADL (primary and secondary endpoints), were administered over the phone if subjects were unable to travel to clinic.

At-home study drug administration has been flagged so as to allow for a comparative safety assessment between in-clinic and at-home dosing. Similarly, phone COAs have been flagged to enable sensitivity analyses including/excluding phone COAs as their quality may be seen as less reliable. Although phone COAs have been explicitly allowed since version one of the protocol, all phone COA assessments were only collected as a result of the COVID-19 pandemic.

Protocol deviations due specifically to the COVID-19 pandemic have been flagged. Each subject's first COVID-19 protocol deviation will be treated as an intercurrent event indicating the earliest timepoint at which a given subject's trial conduct was meaningfully affected by the pandemic. All data points after this first protocol deviation are then flagged as "post-COVID" on a per-subject level and treated as missing for sensitivity analyses. Similarly, sensitivity analyses using a single date applied broadly to all subjects using a sliding window will be used as an alternative means to exclude "post-COVID" data. As mentioned previously, missed study drug administration is treated as a post-randomization event and can be identified as COVID-related or not from the protocol deviation log.

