6. STATISTICAL CONSIDERATIONS AND ANALYSIS PLAN

The efficacy analyses will be based on the modified intent-to-treat population, which is defined as all randomized patients who receive at least one dose of study drug and have at least one postbaseline primary efficacy CDR-SB measurement. For the efficacy analysis, patients will be grouped according to the treatment assigned at randomization.

The safety analysis will be based on all randomized patients who receive at least one dose of either MTAU9937A or placebo, or GTP1. Patients will be grouped according to MTAU9937A treatment actually received.

- A primary analysis will occur after the last patient has completed the Week 73 assessment.
- A final analysis will occur after the last patient has finished the OLE and completed the Week 169 assessment.

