Appendix 1 Schedule of Activities (cont.)

- i Only perform assessment if discontinuation visit is ≥ 16 weeks after last assessment for this instrument or procedure. However, if the patient discontinues study drug because of an infusion-related reaction, concurrent ADA and PK samples will also be collected at 12 weeks after the last administration of study drug.
- j Includes respiratory rate, pulse rate, and systolic and diastolic blood pressure while the patient is in a seated position, and temperature. Record abnormalities observed at baseline on the General Medical History and Baseline Conditions eCRF. At subsequent visits, record new or worsened clinically significant abnormalities on the Adverse Event eCRF. On study drug treatment visits, vital signs should be collected 0–4 hours prior to infusion and 60–90 minutes after completion of infusion.
- k Vital signs should be assessed on the same day(s) that the [^{18}F]GTP1 PET scan and/or LP are performed. Vital signs should be assessed just prior to injection of [^{18}F]GTP1 or initiation of the LP procedure, but no earlier than 1 hour prior to injection of [^{18}F]GTP1 or initiation of the LP procedure. Vital signs should also be assessed just after injection of [^{18}F]GTP1 or conclusion of the LP procedure, but no later than 1 hour after injection of [^{18}F]GTP1 or conclusion of the LP procedure.
- l Includes evaluation of the head, eyes, ears, nose, and throat, and the cardiovascular, dermatological, respiratory, and gastrointestinal systems. In addition, the musculoskeletal and genitourinary systems should be examined as clinically indicated. Record abnormalities observed at baseline on the General Medical History and Baseline Conditions eCRF. At subsequent visits, record new or worsened clinically significant abnormalities on the Adverse Event eCRF.
- m Perform a limited, symptom-directed examination at specified timepoints or as clinically indicated. Record new or worsened clinically significant abnormalities on the Adverse Event eCRF.
- n If amyloid PET is used to confirm amyloid positive eligibility, an LP will not be performed as part of screening. If amyloid PET result suggests a patient is amyloid negative, an LP may be performed as part of screening to re-assess amyloid positivity eligibility on the basis of CSF.

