4.1.1 Modified Intent-to-Treat Population

Efficacy analyses for each endpoint will be performed on the modified intent-to-treat population (mITT). For the primary and each secondary endpoint, the mITT population will include all randomized patients that have both a baseline measurement and at least one post-baseline measurement for the primary endpoint. The treatment groups will be based on the treatment assigned at randomization.

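### The SAP 4.4.3 tipping-point analysis omits dosed patients who have no post-baseline CDR-SB, although SAP 4.4.1 includes them in the population for the effect

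*SAP*

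**What the plan says.** SAP 4.4.3 tests the MAR assumption with a completer analysis, linear extrapolation, last observation carried forward (LOCF) and a tipping point, fitted at Weeks 25, 49 and 73. It says that "sensitivity analyses will be performed in the mITT population for the co-primary and secondary endpoints". (The trial has one primary endpoint, so the word co-primary is a slip; nothing here depends on it.) The fourth method is specified only as "Tipping point analysis", with no imputation model, range of shifts or rule on which arms are shifted.

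The population is described in four places:

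- SAP 4.1.1 defines mITT, for the primary and every secondary endpoint, as "all randomized patients that have both a baseline measurement and at least one post-baseline measurement for the primary endpoint".
- Protocol section 6 also requires that patients "have at least one postbaseline primary efficacy CDR-SB measurement", and adds at least one dose.
- SAP 4.4.1 calls its target the mITT estimand, then says: "It will be estimated using all randomized patients who received at least one dose of study drug". It sets no post-baseline condition.
- SAP 4.4 points to Section 4.1.2 for the mITT definition, but 4.1.2 defines the safety-evaluable set.

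The first scheduled post-baseline CDR is at Week 25. Protocol 4.6.1 places the treatment discontinuation visit 12 weeks (±7 days) after the last dose. The Appendix 1 footnote that governs CDR at that visit reads: "Only perform assessment if discontinuation visit is ≥ 16 weeks after last assessment for this instrument or procedure".

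**The concern.** A dosed patient who leaves before any post-baseline CDR-SB has all of the outcome missing. That patient belongs to the population in SAP 4.4.1 but not to the set in SAP 4.1.1, and no planned analysis imputes a value for them. The MMRM handles them implicitly through MAR, since with no outcome record they add essentially nothing to the fit. The tipping point exists to ask how far MAR must fail before the conclusion changes, and it stays silent on these patients.

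If they are few, little is lost. If they are not, a smaller share of the active arm carries the penalty, and a larger penalty is needed to remove significance. The result would then look more robust than it is for the population in SAP 4.4.1. Early withdrawal that differed by arm would be the kind of departure from MAR that this check should reach.

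**Working it through.** **Who is excluded.** The baseline CDR precedes the first dose by at most about 2 weeks, unless the baseline visit is extended (Appendix 1, footnote a). The time from baseline CDR to the discontinuation visit is then:

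- Last dose at Week 1: 12 weeks, plus up to 1 for the visit window and up to 2 for the baseline visit, so about 15 at most. This is below 16, so no CDR is taken even if the patient attends.
- Last dose at Week 3: 2 + 12 = 14 weeks, and up to about 17 with the same allowances. Borderline.
- Last dose at Week 5: 4 + 12 = 16 weeks on schedule. The rule is met, and it is met more easily after later doses.

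Taking SAP 4.1.1 at face value, any post-baseline CDR-SB qualifies. The patients lost are therefore mainly those who stop after one or two doses or who do not attend that visit.

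**Reproducing the plan's figures (SAP 2.2).** Inputs: 228 pooled active and 137 placebo before dropout, 25% dropout, SD 2, effect 0.6, two-sided alpha 0.05.

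- Remaining patients: 228 × 0.75 = 171 and 137 × 0.75 = 102.75.
- SE = 2 × √(1/102.75 + 1/171) = 0.250.
- Power = Φ(0.6/0.2496 − 1.96) = 67.1%, against 68% stated.
- 90% CI for 4500 mg against placebo: 0.6 ± 1.645 × 2 × √(2/102.75) = 0.14 to 1.06, as stated.

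**Tipping penalty.** Suppose the observed effect is 0.6 and a penalty is applied to each missing active-arm value. Hold the SE fixed and let e, the share of dosed patients with no post-baseline CDR-SB, be equal in both arms.

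- Lower 95% limit: L = 0.6 − 1.96 × 0.2496 = 0.111.
- All dosed patients: share imputed 0.25, so the penalty that removes significance is 0.111/0.25 = 0.44 points.
- mITT: share imputed f = (0.25 − e)/(1 − e), penalty L/f, ratio to the all-dosed figure 0.25/f.

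The documents do not give e, so it is an assumption shown as a range. Counts are e × 457, as if everyone enrolled was dosed.

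| e | Patients | f | mITT penalty | Ratio | Share of missing never imputed (e/0.25) |
|---|---|---|---|---|---|
| 0% | 0 | 0.250 | 0.44 | 1.00 | 0% |
| 2% | 9 | 0.235 | 0.47 | 1.065 | 8% |
| 5% | 23 | 0.211 | 0.53 | 1.19 | 20% |
| 8.3% | 38 | 0.182 | 0.61 | 1.375 | 33% |

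The 8.3% row is 25% × 24/72: dropout accrues evenly, and everyone leaving before Week 25 has no post-baseline CDR. It is an upper-end case because it ignores CDRs taken at the discontinuation visit.

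**The case against.** **Most early leavers stay in mITT.** A reader might infer that everyone leaving before Week 25 escapes imputation. With a constant hazard that would be 1 − 0.75^(25/73) = 9.4%, giving f = 0.172 and a ratio of 1.45. The documents do not support this, because the discontinuation-visit CDR keeps most patients last dosed at about Week 5 or later. If only those leaving before Week 5 are lost and all others attend the visit, e = 1 − 0.75^(4/73) = 1.6%, f = 0.238 and the ratio is about 1.05. This objection stands, and it is why the range starts at zero.

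**The direction is conditional.** SAP 4.4.3 gives no shift or arm rule. If both arms were shifted, or exclusions differed by arm, direction and size could change. This also stands.

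**The other analyses barely change.** A reader might infer that every missing-data analysis is compromised. A completer analysis imputes nobody. Extrapolation is described as "Using linear extrapolation imputation based on the values at baseline and the last week with a non-missing value", which is undefined with baseline data only. LOCF would simply assign zero change. The point concerns the tipping point alone.

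**The conflict may be one of wording.** The SAP 4.4.1 sentence resembles the protocol definition with its second condition dropped, and keeping the analysis set fixed while varying the missing-data assumption is defensible. But baseline-only patients contribute essentially nothing to the MMRM, so widening the set for the tipping point mainly changes which missing values are stressed.

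**Early withdrawal will be visible.** SAP 4.2 tabulates discontinuations and reasons by treatment group, and SAP 4.6 compares missing Week 73 data between arms. Neither imputes the excluded patients. Protocol 1.2.2 reports the drug as generally well tolerated, so differential early withdrawal is a possibility and not something the documents show.

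**Conclusion.** The gap is real but narrow. As written, the tipping point cannot speak for dosed patients with baseline CDR-SB only, although SAP 4.4.1 counts them. On the planning values, the penalty needed to overturn the result is 0.44 points in all dosed patients. In mITT it is the same if nobody is excluded, 6.5% larger at 2% excluded, 19% larger at 5% and 37.5% larger in the upper-end 8.3% case. This rests on an observed effect of 0.6, a fixed SE, a penalty on active-arm missing values only and equal exclusion by arm.

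A reader might go further and conclude that robustness to MAR is certainly overstated, or that the primary estimate is biased. Neither follows. The number excluded is unknown and may be very small, and the MMRM estimate under MAR is essentially the same in either set. The change is still worth making because it is cheap and alters what the robustness check can conclude.

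**What to change.** In SAP 4.4.3, run the tipping point in all randomized, dosed patients with a baseline CDR-SB. For those with baseline data only, multiply impute Weeks 25, 49 and 73 from baseline covariates and arm, then apply the shift to all imputed values. State the range of shifts and which arms receive it.

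Report the number excluded from mITT by arm, so that a reader can see which row of the table applies. Reconcile the mITT definition in SAP 4.1.1, the cross-reference to Section 4.1.2 in SAP 4.4 and the population sentence in SAP 4.4.1.

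A rule for baseline-only patients is needed anyway. SAP 4.4.3 also sets data after certain intercurrent events to missing, which can leave an mITT patient with nothing after baseline.

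The cost is some SAP wording, a little more analysis work and a tipping point that may look less favourable. The primary analysis does not change.

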4.4.4 Subgroup Analyses

Exploratory subgroup analyses of the primary efficacy endpoint will be performed to evaluate the consistency of the primary analysis results across pre-specified subgroups defined by demographic and baseline characteristics. The following subgroups will be analyzed with respect to the primary efficacy endpoint:

- Age (≤ 65 years, > 65 years)
- Sex (male, female)
- Dementia status (prodromal, mild)
- APOE4 status (positive, negative)
- Geographic region (North America, EU, rest-of-world)

Biomarker subgroup analyses are specified in Section 4.4.5.

For above subgroup analyses, a MMRM model as specified for the primary analysis in Section 4.4 will be used for each subgroup analyses based on the available data subset for the patient subgroup of interest with the exception of the dementia status and APOE4 status subgroup analyses (bullets 3 and 4) which will not contain the respective indicator variables since they are being used to define the subgroup.

4.4.5 Biomarker Analyses

Biomarker subgroup analyses

Additional biomarker analyses will be performed to further evaluate the treatment benefit in biomarker-defined patient subpopulations based on baseline levels of tau pathology as measured by [¹⁸F]GTP1 which was collected from roughly 85% of patients at baseline.

Based on the primary and secondary efficacy endpoints, the treatment benefit will be assessed for the following pre-specified biomarker-defined patient subpopulations:

- **[¹⁸F]GTP1 at baseline:** [¹⁸F]GTP1-high patients will be defined as having a temporal meta-ROI SUVR ≥ 1.3 . [¹⁸F]GTP1-low patients will be defined as temporal meta-ROI

SUVR < 1.3 (Jack et al., Brain 2017). From the baseline data, roughly 75% of patients who received a [¹⁸F]GTP1 scan were defined as [¹⁸F]GTP1-high at the baseline visit.

Additional sensitivity analyses will be conducted to assess the robustness of the proposed SUVR threshold and region of interest for defining [¹⁸F]GTP1-high vs low.

An MMRM model similar to that specified for the primary and secondary analyses will be used for each subgroup analysis based on the data subset for the biomarker subgroup of interest. Point estimates for the treatment benefit within each biomarker patient group as defined above will be presented along with 95% confidence intervals and p-values.

Pharmacodynamic biomarker analyses

[¹⁸F]GTP1 has been identified as a key exploratory imaging PD biomarker. [¹⁸F]GTP1 whole cortical gray SUVR change from baseline will similarly be analyzed and reported using the MMRM model described in Section 4.4. In addition to whole cortical gray SUVR, other exploratory [¹⁸F]GTP1 ROIs and metrics of tau spread will be explored.

Several candidate fluid PD biomarkers have been identified (e.g. multiple CSF assays for different tau species and plasma tau measures) and will be measured to assess the effect of MTAU9937A. Descriptive summaries of the PD biomarker values at each visit, as well as changes from baseline will be summarized by treatment arm.

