
 To evaluate the effect of MTAU9937A on time to decline in functional capacity compared with placebo 	
 Time from baseline to change in diagnosis or the occurrence of a decline in functional capacity, as assessed by an AD event inventory and other assessments

Exploratory	
Pharmacokinetic Objectives	Corresponding Endpoints

 To evaluate potential relationships between drug exposure and the safety, PD response, and activity of MTAU9937A 	
 Relationship between serum pharmacokinetics for MTAU9937A and safety endpoints Relationship between serum or CSF pharmacokinetics for MTAU9937A and clinical activity or PD endpoints

 To evaluate potential relationships between selected covariates and exposure to MTAU9937A 	
 Relationship between selected covariates, including but not limited to age, sex, and serum pharmacokinetics for MTAU9937A
Immunogenicity Objective	Corresponding Endpoint

 To evaluate potential effects of ADAs 	
 Relationship between ADA status and efficacy, safety, or PK endpoints
Biomarker Objectives	Corresponding Endpoints

 To evaluate the effect of MTAU9937A on pathological burden of tau To evaluate the effect of MTAU9937A on biomarkers to aid in defining MOA To evaluate the relationship between changes in biomarkers and efficacy To evaluate if biomarkers, at baseline, identify a subset of patients with more rapid disease progression and/or enhanced clinical benefit to MTAU9937A 	
 Changes from baseline in brain tau burden over time as measured by [¹⁸F]GTP1 PET Changes from baseline in levels of soluble tau in plasma or CSF and in levels of other potential disease biomarkers Changes from baseline in brain structure measured by MRI Relationship between changes in efficacy endpoints and measures of changes in brain tau burden, soluble tau in biofluids, brain structure, and other potential disease biomarkers Relationships between biomarkers in blood or CSF (including common and rare genetic variants, identified through genomic analysis on DNA extracted from blood) and efficacy, safety, PK, immunogenicity, or other biomarker endpoints
Resource Utilization Objectives	Corresponding Endpoint

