2.2 DETERMINATION OF SAMPLE SIZE

This study enrolled 457 patients randomized to one of three active IV dose arms or to an IV placebo dose arm in a 2:3:2:3 ratio. This sample size provides reasonable precision for estimating a clinically significant treatment effect on CDR-SB scores when MTAU9937A is compared with placebo. Assuming an observed 0.6-point difference in mean CDR-SB decline between the 4500 mg MTAU9937A arm and placebo at Week 73 (a 40% relative reduction in decline versus placebo), a standard deviation across patients of 2, and a 25% dropout rate, a 90% confidence interval on the population treatment effect point estimate for the CDR-SB is approximately 0.14–1.06.

The primary analysis detailed in Section 4.4 proposes the first hypothesis test for CDR-SB be a comparison between a single pooled 4500 mg and 8100 mg dose arm versus placebo (pre-dropout n = 228 and 137, respectively). Assuming a true 0.6-point difference in mean CDR-SB decline between the pooled MTAU9937A arm and placebo at Week 73 (a 40% relative reduction in decline versus placebo), a standard deviation across patients of 2, and a 25% dropout rate, this hypothesis test is expected to have 68% power at the alpha = 0.05 level.

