Comparisons of efficacy will be performed between each MTAU9937A treatment arm and the placebo group by first pooling data from the middle and high doses for the first statistical test of the primary endpoint and then subsequently testing each treatment arm individually. Thus, there will be four comparisons across the doses:

MTAU9937A dose groups for hierarchical testing:

- **Group 1:** MTAU9937A 4500 mg + MTAU9937A 8100 mg vs placebo
- **Group 2:** MTAU9937A 4500 mg vs placebo
- **Group 3:** MTAU9937A 8100 mg vs placebo
- **Group 4:** MTAU9937A 1500 mg vs placebo

One model pooling middle and high doses will be used to test the Group 1 hypothesis. A second model including all 3 active arms separately will be used for Groups 2-4.

Type I Error Management

Type I error for the primary endpoint will be controlled using a fixed sequence testing procedure at the two-sided 5% significance level. The testing procedure will proceed with comparisons following the order across the four dose groups detailed above. After the first hypothesis test, each subsequent hypothesis will only be formally tested if the preceding one is significant at the 5% level.

For each dose group that has a significant result for the hypothesis test for the primary endpoint, a separate fixed sequence testing procedure will be ungated for that dose group's secondary endpoints that will similarly proceed at the 5% level. The overall testing procedure is detailed visually in the table below.

		MTAU9937A Dose group			
Endpoint		Group 1	Group 2	Group 3	Group 4
Primary	Change in CDR-SB score from baseline to Week 73				
Secondary	1. Change in ADAS-Cog13 score from baseline to Week 73	↓	↓	↓	↓
	2. Change in ADCS-ADL score from baseline to Week 73	↓	↓	↓	↓
	3. Change in RBANS total score from baseline to Week 73	↓	↓	↓	↓
	4. Change in Amsterdam iADL score from baseline to Week 73	↓	↓	↓	↓

No control for type I error will be applied for the exploratory endpoints, including sensitivity, subgroup, and biomarker analyses. Efficacy analyses will not involve formal comparisons between the MTAU9937A treatment arms.

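### The SAP estimates treatment benefit separately in tau-high and tau-low patients but never the difference between them, so a uniform effect can appear as benefit in tau-high patients only

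*SAP*

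**What the plan says.** SAP 4.4.5 classes patients as GTP1-high or GTP1-low at a temporal SUVR of 1.3. It fits an MMRM to each subset for the primary and secondary endpoints, and specifies the output: "Point estimates for the treatment benefit within each biomarker patient group as defined above will be presented along with 95% confidence intervals and p-values".

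SAP 4.4.4 takes the same route for age, sex, dementia status, APOE4 status and region on the primary endpoint, with one MMRM per data subset. Its purpose is "to evaluate the consistency of the primary analysis results across pre-specified subgroups". It does not mention p-values.

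The protocol's biomarker objectives (Section 2, Table 1) include whether baseline biomarkers "identify a subset of patients with more rapid disease progression and/or enhanced clinical benefit to MTAU9937A".

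The model in SAP 4.4 has two interactions: APOE4 status by dementia status, and treatment by visit. Neither document has a treatment-by-subgroup term or any other estimate of how far the treatment effect differs between subgroups. SAP 4.4 labels the subgroup and biomarker analyses exploratory and applies no type I error control to them.

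**The concern.** Consistency across subgroups and enhanced benefit in one of them are both questions about a difference between two treatment effects. (The other half of the protocol objective, faster progression, is prognostic and is not at issue here.) The planned output gives two separate effects and leaves the reader to compare them. For the tau split, the most visible thing to compare is a pair of p-values.

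That comparison is lopsided. About three quarters of scanned patients are tau-high, so the tau-high estimate has a much smaller standard error. The same true effect can therefore be significant in one group and not in the other through sample size alone. In a study that Protocol 1.4 describes as proof of concept, what is at stake is whether the report can support a statement that the drug works better, or only, in tau-high patients.

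**Working it through.** **Inputs**

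- Effect, SAP 2.2: "Assuming a true 0.6-point difference in mean CDR-SB decline between the pooled MTAU9937A arm and placebo at Week 73".
- Variability and loss, SAP 2.2: "a standard deviation across patients of 2, and a 25% dropout rate".
- Pooled active and placebo, SAP 2.2: "pre-dropout n = 228 and 137, respectively".
- Arms for the single-dose checks, SAP 2.2: "This study enrolled 457 patients randomized to one of three active IV dose arms or to an IV placebo dose arm in a 2:3:2:3 ratio", giving about 137 for 4500 mg and for placebo, and about 91 each for 8100 and 1500 mg.
- Test level, SAP 4.4: "controlled using a fixed sequence testing procedure at the two-sided 5% significance level".
- Tau PET, SAP 4.4.5: about 85% scanned at baseline, and about 75% of those tau-high.

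**Assumptions that the documents do not give:** SD, dropout and allocation are the same in both tau groups; a normal approximation on completers is adequate.

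**Formulas:** SE = SD × √(1/n₁ + 1/n₀); power = Φ(δ/SE − 1.96) + Φ(−δ/SE − 1.96).

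**Step 1: reproduce the SAP's power.** Completers are 228 × 0.75 = 171 and 137 × 0.75 = 102.75. SE = 2 × √(1/171 + 1/102.75) = 0.250, and 0.6/SE = 2.40. Power = 67.1%, against the SAP's 68%. The formula is adequate for what follows.

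**Step 2: apply it to each tau group.** The tau-high fraction of each arm is 0.85 × 0.75 × 0.75 = 0.478. The tau-low fraction is 0.85 × 0.25 × 0.75 = 0.159.

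| | Tau-high | Tau-low |
|---|---|---|
| Completers, active / placebo | 109.0 / 65.5 (about 175) | 36.3 / 21.8 (about 58) |
| SE | 0.313 | 0.542 |
| Power at 0.6 | 48.4% | 19.7% |

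**Step 3: joint outcomes.** The groups contain different patients, so the two results are independent.

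- Tau-high only: 0.484 × (1 − 0.197) = about 39%
- Tau-low only: 0.197 × (1 − 0.484) = about 10%
- Both: 0.484 × 0.197 = about 9.5%
- Neither: the remainder, about 41.5%

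Among trials with any significant tau group, 38.8/(38.8 + 10.2 + 9.5) = 66% show tau-high only, although the effect is identical.

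**Step 4: range of tau-high only.**

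- Effect, pooled doses: 14.6% at 0.3, 26.2% at 0.45, 50.7% at 0.9.
- SD at effect 0.6: 43.6% at SD 1.8, 32.4% at SD 2.3.
- No dropout: 45.2%.
- Single doses at 0.6: 33.7% for 4500 mg, 28.8% for 8100 or 1500 mg. The SAP does not say which dose comparison the subgroup analyses use.

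**Step 5: the between-group contrast.** SE = √(0.313² + 0.542²) = 0.625, so the 95% half-width is 1.96 × 0.625 = 1.23 points. Under a uniform effect it is falsely significant 5% of the time. In simulation, it was significant in 5.8% of the trials that showed tau-high only. Power for a true 0.6-point difference is 16%. For 80% power the true difference must be about (1.96 + 0.84) × 0.625 = 1.75 points.

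**The case against.** The strongest reply is that these analyses are declared exploratory, carry no error control and have no decision rule attached. SAP 4.4.5 asks about benefit within tau groups, and the consistency aim belongs to SAP 4.4.4. Confidence intervals are planned alongside the p-values, and the tau cut-off and region get sensitivity analyses. Because the subsets are disjoint, anyone can compute the difference and its standard error from the planned output. And the contrast is weak: with 16% power for a 0.6-point difference, it will rarely settle anything.

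Much of this stands. The gap is in estimation and reporting; no information is lost. Neither document says that subgroup p-values will be compared, so the misreading is a risk and not a planned step. Removing the p-values alone would change little, since an interval that excludes zero in tau-high and includes it in tau-low is the same event.

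What does not stand is that exploratory status closes the matter. The protocol lists enhanced benefit as an objective and SAP 4.4.4 names consistency as its purpose, yet the planned output answers neither. The contrast's imprecision is itself worth reporting, because two separate intervals do not show it directly.

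**Conclusion.** The plan lacks an estimate of the between-subgroup difference that its own aims call for. At the SAP's planning effect, a drug that works equally in both tau groups gives a tau-high-only result in about 39% of trials, roughly four times as often as the reverse. This rests on equal SD, dropout and allocation in the two tau groups and on a completers approximation; MMRM may be somewhat more precise. No figure is given for the SAP 4.4.4 factors, because the documents do not state those subgroup sizes.

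A reader might infer more than this, and the documents do not support it:

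- **That every subgroup is judged by its own p-value.** P-values are specified only for the tau split.
- **That tau-high only is the most probable outcome.** At 39% it comes slightly behind neither group being significant (41.5%), and it is much less frequent at small effects.
- **That an ineffective drug would often show the pattern.** With no effect, tau-high-only benefit occurs in about 0.025 × 0.95 = 2.4% of trials per comparison, much the same as the 2.5% in which an interaction test falsely favours tau-high. The problem arises when there is a real, uniform effect.
- **That the primary conclusion is at risk.** The fixed-sequence test and its type I error are untouched.

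**What to change.** For the GTP1 split, on each endpoint analysed, and likewise for each SAP 4.4.4 factor, add the Week 73 difference in treatment effect between subgroups with its 95% CI. State which dose comparison is used. Either route serves:

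- one MMRM with treatment-by-visit-by-factor terms and their lower-order terms, letting the covariance matrix and covariate slopes differ by subgroup; or
- the difference of the two planned estimates, with SE = √(SE₁² + SE₂²).

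Region has three levels and needs two contrasts against a reference. Keep the within-group estimates and CIs. State in the SAP that any claim of enhanced or differential benefit will rest on the contrast and not on comparing within-group p-values.

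The cost is a few lines of code on data already collected. The single model needs the flexibility above, since without it it imposes a common covariance and common slopes that separate models do not. The contrast is also imprecise, so the SAP should add that a non-significant contrast is not evidence of consistency and that the interval must be reported with it.
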